7.4.1.2 Secondary Analysis

The primary analysis will be repeated for completers only, i.e. without utilizing LOCF imputation for subjects with missing Week 12 values. Additionally, Week 4 and Week 8 values will be analyzed similarly to End of Treatment.

An analysis of change from baseline in mean number of micturitions per day using a Mixed Model Repeated Measures (MMRM) with age group, geographic region, time (visit), and a time-by-treatment interaction as factors and the number of micturition episodes at baseline as covariate will serve as another sensitivity analysis. The repeated measures model will present LS means and two-sided 95% CIs for changes from baseline within each treatment group.

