7 STATISTICAL METHODOLOGY

The statistical analysis will be coordinated by the responsible biostatistician of Astellas. A Statistical Analysis Plan (SAP) will be written to provide details of the analysis, along with specifications for tables, listings and figures to be produced. The SAP will be finalized before database softlock at the latest. Any deviations from the analysis planned in SAP will be justified in the Clinical Study Report (CSR).

Prior to Database Lock, a Final Review of Data and TLFs Meeting will be held to allow a review of the clinical trial data and to verify the data that will be used for analysis set classification. If required, consequences for the statistical analysis will be discussed and documented. A meeting to determine analysis set classifications may also be held prior to database hard lock.

In general, baseline is defined as the last measurement before the first dose of double-blind study drug. For variables based on the electronic diary, the 3 days of the diary recorded prior to Visit 2/Baseline (Week 0) will be used to derive these variables at baseline just as the 3 diary days before each post-baseline visit will be used to derive these variables at these visits.

The End of Treatment (EOT) visit is defined as the last post-baseline visit during the double-blind study period for which data is available. The EOT visit value for diary variables is the average or number of the diary measurements for Week 12, as applicable. If no Week 12 diary data measurements are available, then the last available earlier post-baseline average or number of the diary measurements within a designated visit window will be used (LOCF). Data from the EOT visit will be analyzed to account for subjects prematurely terminating the study and is regarded as the primary visit. The EOT visit will be Week 12/EOT (Visit 5) for subjects who complete the study.

All statistical comparisons will be made using a two-sided test at $\alpha = 0.05$ significance level and confidence intervals (CIs) will be reported with a coverage consistent with this significance level unless specified otherwise.

All efficacy and safety variables will be summarized using descriptive statistics. Continuous variables will be summarized using the descriptive statistics number of non-missing observations (N), mean, standard deviation (SD) or standard error (SE), minimum, median, and maximum unless specified otherwise. Categorical variables will be described using N and percent.

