7.4 Analysis of Efficacy

Efficacy analysis will be conducted on the FAS and PPS. Incontinence episodes will be analyzed with the FAS-I. The interpretation of results from statistical tests will be based on the FAS.

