7.4.1 Analysis of Primary Endpoint

7.4.1.1 Primary Analysis

The primary efficacy variable is change from baseline to end of treatment in mean number of micturitions per day based on a 3-day electronic diary. The primary analysis will be performed for the FAS at the EOT visit, i.e. Week 12 for subjects who complete the study or last post-baseline visit during the double-blind study period for subjects who discontinue early.

The hypothesis for comparison is as follows:

H0: Difference between mirabegron and placebo in change from baseline to end of treatment in mean number of micturitions per day based on a 3-day electronic diary is 0.

H1: Difference between mirabegron and placebo in change from baseline to end of treatment in mean number of micturitions per day based on a 3-day electronic diary is not equal to 0.

Change from baseline to end of treatment in mean number of micturitions per day will be analyzed using Analysis of Covariance (ANCOVA). The response variable will be the mean change in number of micturition episodes per day from baseline to end of the study with treatment group, geographic region, and age group as fixed factors and baseline as a covariate. Within the framework of this ANCOVA model, LS means and two-sided 95% CIs for the mean change from baseline within each treatment group will be provided. Differences in LS means between mirabegron and placebo will be derived together with 95% CIs and p-values. Further details may be found in the SAP.

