7.5.3 Vital Signs

Pulse rate, systolic blood pressure, and diastolic blood pressure will be summarized by treatment group using descriptive statistics (mean, standard deviation, minimum, maximum and median) for baseline value, post-baseline time point values (Week 4, Week 8, and Week 12/EOT), and change from baseline to each post-baseline time points. The average change from baseline to end of treatment for each vital sign variable will be analyzed using the ANCOVA model with treatment group and geographic region as fixed factors and baseline vital sign value as covariate. Results will be summarized separately for office based measurements and HBPM. No p-values will be calculated.

An analysis of change from baseline of vital signs using a Mixed Model Repeated Measures (MMRM) model with geographic region, age group, time (visit), and a time-by-treatment interaction as factors and the baseline values as covariate will serve as another sensitivity analysis. The repeated measures model will present LS means and two-sided 95% CIs for changes from baseline within each treatment group.

Number and percentage of subjects with more than 2/5/10/15/20 mmHg increase from baseline in SBP, more than 2/5/10/15 mmHg increase in DBP or more than 5/10/15 bpm increase from baseline in pulse rate, on 2 consecutive post-baseline visits will be summarized by treatment group. Number and percentage of subjects with vital sign values shifting between JNC-7 defined risk categories will be summarized by treatment group. These categories are listed below:

Category	Systolic BP (mm Hg)	Diastolic BP (mm Hg)
Normal	< 120	<80
Prehypertension	120-139	80-89
Hypertension Stage 1	140-159	90-99
Hypertension Stage 2	\geq 160	\geq 100

Number and percentage of subjects with a PR > 100 bpm at any office visit or by HBPM will be summarized by treatment group separately.

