7.10 Handling of Missing Data, Outliers, Visit Windows, and Other Information

For efficacy variables and vital sign data, analysis at End of Treatment will take into account subjects who withdraw before Week 12 and therefore do not have efficacy measurements available for that visit. The End of Treatment analysis is a Last Observation Carried Forward (LOCF) approach. As a secondary analysis, a mixed model repeated measures analysis will be performed for selected variables as described in Sections 7.4.1 and 7.4.2

Other imputation rules to account for missing data will be described in the SAP.

Subjects do not always adhere strictly to the visit timing the protocol. Visit windows around the target days for each visit will be defined in the SAP.

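### Does the MMRM fail as a sensitivity analysis because only within-group estimates are listed as its output?

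*Protocol*

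**What the plan says.** Protocol section 7.4.1.1 sets a two-sided hypothesis about the difference between arms in change from baseline to end of treatment in micturitions per day. Its ANCOVA yields within-group LS means with 95% CIs and then the contrast: "Differences in LS means between mirabegron and placebo will be derived together with 95% CIs and p-values". Under section 7, a missing Week 12 diary value is replaced by the last earlier post-baseline value.

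Section 7.4.1.2 plans two checks on that result. The first is an ANCOVA without LOCF: "The primary analysis will be repeated for completers only, i.e. without utilizing LOCF imputation for subjects with missing Week 12 values". The second is an MMRM with age group, region, visit and visit-by-treatment as factors; the model with "number of micturition episodes at baseline as covariate will serve as another sensitivity analysis". Its output is described in one sentence: "The repeated measures model will present LS means and two-sided 95% CIs for changes from baseline within each treatment group". The same sentence closes the MMRM paragraph for the patient-reported outcomes in 7.4.2 and the one for vital signs in 7.5.3. Section 7.10 refers back to these paragraphs without adding an output: "As a secondary analysis, a mixed model repeated measures analysis will be performed for selected variables".

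Section 7 states that the SAP will give the analysis details and the specifications for tables, listings and figures, and that it will be final before database softlock at the latest.

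**The concern.** A sensitivity analysis should report the same quantity as the analysis it checks. Here the primary quantity is a between-arm difference, whereas the only output listed for the MMRM is one interval per arm. Elsewhere the authors did name differences where they wanted them: for the primary ANCOVA in 7.4.1.1 and for the Poisson model in 7.4.2. The omission could therefore be read as deliberate.

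The MMRM also has a role that the completers analysis cannot fill. Diaries cover the three days before each visit, and the increase from 25 mg to 50 mg takes place at Visit 3. A mirabegron subject whose last diary is Week 4 therefore enters the LOCF analysis with a value recorded on 25 mg. The completers analysis drops that subject, while the MMRM keeps him without carrying the value forward. If the MMRM gave no contrast, no check that retains early leavers would show directly whether the primary difference depends on LOCF. A reader left with two intervals might also judge by whether they overlap, which is a stricter criterion than the planned test.

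**Working it through.** **Inputs (Protocol 7.1 and synopsis).** SD of change 2.7; planned difference 0.65; two-sided alpha 0.05; 272 evaluable and 320 randomized per arm. Normal approximation, without covariate adjustment.

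**The protocol's own figure.**
- SE of the difference at 272 per arm: 2.7 × √(2/272) = 0.2315.
- Power at 0.65: Φ(0.65/0.2315 − 1.96) = 0.802. The stated 80% is reproduced. The two-sample t-test needs 271.8 per arm, hence 272.

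**Within-group intervals against the between-arm test.**
- Within-group half-width: 1.96 × 2.7/√n, which is 0.321 at 272 and 0.296 at 320.
- The two intervals separate at twice that: 0.642 and 0.592.
- The between-arm test is significant from 1.96 × 2.7 × √(2/n): 0.454 and 0.418.
- The ratio is √2 at any n or SD with equal arms. Separation of the intervals corresponds to a two-sided p of about 0.006.

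**At a true difference of 0.65.**

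| Per arm | Test significant | Intervals separate | Significant but overlapping |
|---|---|---|---|
| 272 | 80.2% | 51.4% | 80.2 − 51.4 = 28.8% |
| 320 | 86.1% | 60.8% | 86.1 − 60.8 = 25.3% |

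The last column would matter only if someone judged the MMRM by overlap. No section proposes that rule. The hypothesis in 7.4.1.1 concerns the difference, and 7.4 fixes where conclusions come from: "The interpretation of results from statistical tests will be based on the FAS".

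**Can the model give the contrast?** Yes. With three post-baseline visits and two arms there are 3 × 2 = 6 cell means. Visit (3 parameters) plus visit-by-treatment (3 more) fits all six, even though no separate treatment main effect is listed. The Week 12 difference is therefore a standard contrast of the planned model.

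**Is it lost from the listed output?** No. The point estimate is the Week 12 LS mean for mirabegron minus that for placebo, both of which are reported. Treating the two estimates as nearly independent, the half-width of the difference is √(0.321² + 0.321²) = 0.454, the same value as the direct calculation above. Shared covariates make this approximate in the fitted model, but only slightly so in a 1:1 randomized trial of this size.

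**Does the text exclude it?** The sentence says what the model will present; it contains no *only*. Where the protocol wants to withhold inference it says so, as in the ANCOVA paragraph for vital signs in 7.5.3: "No p-values will be calculated". The efficacy MMRM paragraphs carry no such statement. That the same output sentence recurs for three quite different groups of variables points to template text rather than to a decision about the contrast.

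**The case for a change.** The best case for acting is that the protocol is not silent: it names an output, and the output named does not match the hypothesis. The neighbouring models show that the authors knew how to ask for a difference. Naming it in advance would cost one sentence and would remove any later choice about whether to show it. It would also give a direct non-LOCF contrast that keeps early leavers.

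Much of this is true. The mismatch in wording is real, and an explicit Week 12 difference with a 95% CI would read better. But the room for later choice is small. The model, the covariates and the visit are fixed, and the two LS means that determine the estimate must be reported. The remaining freedom is whether one derived row appears in a table, which is the kind of specification section 7 leaves to the SAP. The SAP is not at hand and may already contain it.

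The gap is also narrower than it looks, because a non-LOCF between-arm test at Week 12 is planned in completers. Section 7.4.1.2 further analyses Weeks 4 and 8 in the same way, which gives contrasts at the visits whose values LOCF carries forward. Neither estimates Week 12 for early leavers, so the MMRM keeps its own role, but the primary result does not rest on it alone.

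Extending the request to the patient-reported outcomes would have a cost. MMRM p-values there would be a second set beside the planned ANCOVA tests, over many scores and subscales, with no multiplicity adjustment stated in the protocol.

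**Conclusion.** No change to the plan is needed. Followed as written, the primary analysis still tests the between-arm hypothesis at two-sided 0.05 with the stated 80% power at 272 per arm, and nothing in the MMRM paragraph alters that result or its interpretation. The listed output already fixes the point estimate of the missing contrast and, to a close approximation, its interval. The possible misreading is confined to observed differences between about 0.45 and 0.64 at 272 per arm (0.42 and 0.59 at 320), and it requires an overlap rule that the protocol does not contain.

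These limits rest on the protocol's SD of 2.7 without baseline adjustment. A smaller residual SD would shrink both in proportion and leave their ratio unchanged. The conclusion also assumes that the analysts read the output sentence as a minimum and report the Week 12 difference, which is usual for a model fitted with a visit-by-treatment term. How far LOCF itself might shift the primary estimate is a separate question; the protocol gives no dropout pattern or visit-by-visit effects from which to size it, and it does not bear on whether this sentence is adequate.

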7.4.1.3 Subgroup Analysis

Subgroup analyses will include analyses by geographic region, age group, by previous OAB medication, and reason for treatment termination if previously treated. If sample sizes are sufficient, subgroup analyses by race will be performed. More details on subgroup analyses will be provided in the SAP.

7.4.2 Analysis of Secondary Endpoints

Secondary variables are change to end of treatment in mean incontinence episodes per day, mean volume voided per micturition, mean number of urgency episodes (grade 3 and 4) per day, IPSS total score and subscales (Voiding, Storage, and Quality of Life), Symptom Bother and Total Health related quality of life scores as assessed by OAB-q questionnaire (and subscales), TUFS, PPBC, EQ-5D-5L, and TS-VAS.

An analysis of change from baseline in PRO values using a Mixed Model Repeated Measures (MMRM) with geographic region, age group, time (visit), and a time-by-treatment interaction as factors and PRO value at baseline as a covariate will serve as a sensitivity analysis. The repeated measures model will present LS means and two-sided 95% CIs for changes from baseline within each treatment group.

Analysis of mean change in number of incontinence episodes per day from Baseline to End of Treatment will be performed on the FAS-I using ANCOVA model, p-values will be calculated by stratified ranking ANCOVA. The response variable is standardized ranks on change from Baseline to End of Treatment, with Baseline standardized ranks as covariates and geographic region as a stratum. Standardized ranks are used to adjust for differences in the number of subjects at each geographic region. Further details may be found in the Statistical Analysis Plan.

The number of incontinence episodes and protective garment use during the 3-day diary period will be analyzed using a mixed effects Poisson regression model with treatment group, age group, and geographic region as factors and number of incontinence episodes at baseline as a covariate. Differences in LS means between mirabegron and placebo will be calculated together with 95% CI.

Other secondary efficacy variables will be analyzed using the same ANCOVA model as described for micturitions (refer to Section [7.4.1.1](#)). Descriptive analyses of the EQ-5D-5L will be in the Clinical Study Report. Other planned utility indices and analyses will be calculated in a separate report from the Statistical Analysis Plan and Clinical Study Report.

Responder analyses will be performed for 50% reduction in micturition frequency and for number of subjects with less than 8 micturitions per day at End of Treatment.

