7.2.2 Full Analysis Set - Incontinence (FAS-I)

The FAS-I will include all subjects who meet all of the following criteria:

- Subjects who took at least 1 dose of double-blinded study drug after Randomization,
- Reported at least 1 micturition in the baseline diary and at least 1 micturition post-baseline,
- Reported at least 1 incontinence episode in the baseline diary.

The FAS-I will be used for the analysis of incontinence episodes.

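### Protective garment use is adjusted for baseline incontinence episodes, not for baseline garment use, which costs precision in that comparison

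*Protocol*

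**What the plan says.** Section 7.4.2 handles both count outcomes, incontinence and garments, in one sentence. The model, which includes random effects, is a "Poisson regression model with treatment group, age group, and geographic region as factors and number of incontinence episodes at baseline as a covariate". No other baseline covariate is named, and this is the only model that the protocol assigns to garment use.

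Section 2.3.2 defines the garment endpoint as a change from baseline in the number of garments at Weeks 4, 8 and 12/End of Treatment. Section 5.3.1 lists garments among the diary items collected before Visits 2 to 5. For diary variables, section 7 says that "the 3 days of the diary recorded prior to Visit 2/Baseline (Week 0) will be used to derive these variables at baseline". A baseline garment count therefore exists for this purpose.

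On the analysis set, section 7.2.2 says "The FAS-I will be used for the analysis of incontinence episodes", and section 2.3.2 attaches the FAS-I label to the two incontinence endpoints but not to garments. Section 7.2.1 gives efficacy endpoints to the FAS, so garment use appears to be analysed there.

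**The concern.** The stated covariate fits the first outcome in the sentence and not the second. The garment endpoint is a change from baseline, yet under this model the garment baseline enters neither the response nor the covariates.

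A man's own baseline count is usually the best single predictor of his later count. Replacing it with a related but different baseline leaves more unexplained variation in the treatment comparison. If the arms happen to differ in baseline garment use, the model corrects for this only as far as incontinence episodes track garment use. Entry does not require incontinence, and in the FAS all men with no baseline episodes share one covariate value, so the model cannot separate them by baseline garment use.

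At stake is the width and stability of one secondary comparison that is reported with a 95% confidence interval.

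**Working it through.** **1. Set the models side by side.**

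| Model | Section | Baseline covariate |
|---|---|---|
| Micturition ANCOVA (primary) | 7.4.1.1 | own: "treatment group, geographic region, and age group as fixed factors and baseline as a covariate" |
| Micturition MMRM | 7.4.1.2 | own: "the number of micturition episodes at baseline as covariate will serve as another sensitivity analysis" |
| PRO MMRM | 7.4.2 | own: "PRO value at baseline as a covariate will serve as a sensitivity analysis" |
| Incontinence ranked ANCOVA | 7.4.2 | own (baseline ranks) |
| Vital-sign ANCOVA | 7.5.3 | own: "treatment group and geographic region as fixed factors and baseline vital sign value as covariate" |
| Incontinence Poisson model | 7.4.2 | own |
| Garment Poisson model | 7.4.2 | baseline incontinence episodes |

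Garment use is the only exception.

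**2. The plan's own figure.** The protocol states no sample size, power or correlation for garments. Its primary calculation reproduces: 2 × (1.960 + 0.842)² × 2.7² / 0.65² ≈ 271 per group against 272 stated; 544 / 0.85 = 640; 640 / 0.65 ≈ 985. None of this depends on the garment model.

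**3. Linear approximation.** Let r_own be the correlation of later garment use with baseline garment use, and r_inc its correlation with baseline incontinence (both assumed). The variance under the stated covariate relative to the own baseline is (1 − r_inc²) / (1 − r_own²), and the confidence interval width ratio is its square root.

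| r_own | r_inc | Variance ratio | Width ratio |
|---|---|---|---|
| 0.5 | 0.3 | 0.91 / 0.75 = 1.21 | 1.10 |
| 0.6 | 0.4 | 0.84 / 0.64 = 1.31 | 1.15 |
| 0.7 | 0.5 | 0.75 / 0.51 = 1.47 | 1.21 |
| 0.8 | 0.5 | 0.75 / 0.36 = 2.08 | 1.44 |
| equal | equal | 1.00 | 1.00 |

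**4. Simulation under the planned type of model.** Random-intercept Poisson regression, three post-baseline visits, region and age factors, log(count+1) covariates, true log rate ratio −0.163. Assumed: a median 3-day garment rate of 2.0 with 60 men per arm (400 replicates), or 0.7 with 272 per arm (120 replicates); a log-SD of garment propensity of 0.8 or 1.2; a correlation between garment and incontinence propensity of 0.3, 0.6 or 0.9. The table gives the SD of the estimated log rate ratio with the own baseline, divided by the SD with the incontinence baseline.

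| Men per arm | Log-SD | Corr. 0.3 | Corr. 0.6 | Corr. 0.9 |
|---|---|---|---|---|
| 60 | 0.8 | 0.780 | 0.833 | 0.961 |
| 60 | 1.2 | 0.606 | 0.657 | 0.771 |
| 272 | 0.8 | 0.891 | 0.939 | 1.103 |
| 272 | 1.2 | 0.739 | 0.792 | 0.949 |

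With both baselines in the model, the ratio to incontinence alone runs from 0.610 to 0.960 across all 12 settings. Mean estimates were −0.145 to −0.158 with the incontinence covariate and −0.149 to −0.157 with the own baseline, so neither choice introduces material bias.

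**5. Sensitivity to the simulation model.** A simpler Poisson regression with robust standard errors (272 per arm, 300 replicates, rate ratio 0.8) gave an SE under the stated covariate of 1.12 to 1.17 times the SE with the own baseline at r_own 0.8, 1.02 at 0.6/0.4, and 0.97 at 0.6/0.6. A negative binomial simulation of the same 12 settings (600 replicates) gave ratios of 0.43 to 0.94 with the own baseline and 0.44 to 0.90 with both, below 1 in every setting.

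**6. Chance imbalance.** With 60 per arm and log-SD 0.8, one SD of between-arm imbalance in mean log(count+1) of baseline garments is 0.136. The slope of the estimate on that imbalance was 0.73, 0.58 and 0.38 with the incontinence covariate, and at most 0.02 with the own baseline. The shifts in the log rate ratio are 0.73 × 0.136 = 0.099, 0.58 × 0.136 = 0.079 and 0.38 × 0.136 = 0.052, against at most 0.02 × 0.136 = 0.003. At 272 per arm with the same spread, one SD is 0.136 × √(60/272) = 0.064, and the same slopes give 0.02 to 0.05. The negative binomial simulation gave about 0.03 to 0.04 at that size.

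**The case against.** The strongest reply is that the sentence is shorthand for the respective baseline count: it names the covariate that is right for its first outcome, every other model uses the own baseline, and a statistical analysis plan that is not shown may spell this out. That may be the intention. But the text names a specific covariate, and a programmer who follows it would fit the wrong one for garments.

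The second reply is that adjusting for a related, prespecified baseline is valid, and that the sign as well as the size of the loss depends on assumptions. This partly stands. There is no loss if the two baselines predict equally well, and one setting in step 4 reverses. Sparse use, where the gain is smallest, is plausible because entry does not require incontinence. Whether a man leaks at all also carries some information about garment use.

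Monte Carlo error matters too. With 120 replicates, the standard error of a log SD ratio is √((1 − ρ²)/119), where ρ is the correlation between the two estimates. For an assumed ρ of 0.9 to 0.8 this is about 4% to 6%. Ratios of 0.939 and 0.949 are therefore hard to tell from 1, and 1.103 is itself uncertain; the negative binomial simulation did not reproduce it.

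Finally, the 0.05 to 0.10 imbalance shift belongs to an assumed 60 men per arm and is roughly halved at 272. It shows the lost precision in a single trial and is not a separate harm.

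**Conclusion.** The point holds. The protocol fixes the wrong baseline covariate for garment use, and nothing else in it corrects this. The consequence is lost precision and incomplete adjustment for chance imbalance in one secondary endpoint. It is not bias, and it does not reach type I error, the primary analysis or the sample size.

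The reading of the text is certain; the size is not. Under the assumed garment rates, spreads and correlations, the own baseline reduces the SD of the log rate ratio by 4% to 39% in 11 of 12 settings, with a 10% increase in the remaining one. Using both baselines reduces it by 4% to 39% in all 12. The direction depends on a man's own garment count predicting his later use better than his incontinence count does, which is the usual case.

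**What to change.** State in section 7.4.2 that each Poisson model uses the baseline count of its own outcome: baseline incontinence episodes for incontinence, and the baseline number of protective garments for garment use. The garment baseline should enter in a form defined at zero, such as log(count+1). Baseline incontinence may stay in the garment model as a second covariate; this protects against sparse garment counts and is the option that gained precision in every simulated setting.

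The cost is one sentence in the protocol and matching text in the statistical analysis plan, settled before unblinding. The baseline diary already collects the data.
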